### 7.2.3 Exploratory analyses

#### Successful tumour cell culture rate from surgical samples

The successful cell culture rate is the percentage of cultures in which  $\geq 70\%$  of viable tumour cells plated post-isolation on day 0 are still alive on day 3 in the control hydrogels (cultures with no treatment) compared to the number of tumour samples ( $\geq 0.4g$ ) arriving uncompromised within 24 hours of collection to the Pear Bio laboratory.

### Successful immune cell culture rate from blood samples

The successful cell culture rate is the percentage of cultures in which  $\geq 70\%$  of viable immune cells plated post-extraction on day 0 are still alive on day 3 in the control well (no treatment) compared to the number of blood samples ( $\geq 40\text{mL}$ ) arriving uncompromised within 24 hours of collection to the Pear Bio laboratory.

### Correlating *ex vivo* tumour culture or multi-omic biomarkers to real-world patient outcomes

For any cases where patient outcomes are available or become available prospectively, such as recurrence post-surgery, potential predictive or prognostic biomarkers will be identified. As this data will be sparse, the analysis will only be used to generate hypotheses for future trials, if they present themselves.

### Assessing response to experimental therapies

Observing differentiated *ex vivo* treatment response across the therapies/combos tested on each patient's tumour sample (intra-patient sample comparison)

- a. Ranking of regimen efficacy will be done for each assay metric on a per patient basis to determine agreement/disagreement between assay metrics
- b. Calculating the range of response to all tested regimens for each assay metric on a per patient basis

## **7.3 Interim analysis and study termination**

Interim analysis will be done on laboratory research milestones, such as confirmation of a successful hydrogel formulation to culture brain tumour cells after testing the first 5 patient samples. This interim analysis will be used to allocate samples for research based on the most pressing requirements for *ex vivo* model validation (e.g., hydrogel formulation, drug dosing, etc.).

On recruitment of the first 10 patients, the TMG will meet to assess whether monthly recruitment targets are met and to confirm sample quality and successful culture rates upon receipt and processing at the Pear Bio lab. The TMG will use the results to determine whether to increase accrual up to a maximum of 50 patients.

## **7.4 End of study definition**

The end of the trial is defined as the last patient's last data at a maximum of 12 months post-surgery (outstanding data sent to Pear Bio or final laboratory readout, whichever happens later). In cases of early termination of the trial (e.g., due to slow accrual) or a temporary halt, the Sponsor will notify the REC within 15 days of the decision, and a detailed written explanation for the termination/halt will be given.

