### **1.2.2 Treatment response in malignant primary brain tumours**

Primary brain tumours have a 5-year survival rate of only 12%, and GBM has a median survival of 15 months with aggressive multimodal treatment (5). However, there is some evidence to support use of combined chemotherapy in newly diagnosed patients with GBM, uncertainty about chemotherapy regimen choice in grade 2 and 3 gliomas, and uncertainty about therapy choice at relapse across all gliomas.

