## 2.2 Secondary objectives and endpoints

Secondary objectives	Endpoints

Assess the accuracy of Pear Bio's assay at correlating to patient progression free survival (PFS)
	
Tumour response will be measured as clinically indicated (typically every 3 months), and at all subsequent timepoints until disease progression, as per standard of care.
 
Disease progression is evaluated by the patient's radiologist and is defined by RANO guidelines.
 
Kaplan–Meier curves will be generated on the patient population, and where feasible, based on their line of treatment and for each therapeutic option (if n is sufficient). These curves will be compared to reported data to determine how representative the patient population is of past trials and clinical practice.
 
Computer vision biomarkers will be categorised into low/high groups to determine their correlation with PFS. This analysis will not demonstrate the patient benefit of using Pear Bio's tool, but it will generate hypotheses for interventional trials designed to demonstrate patient benefit.

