## 2.3 Exploratory objectives and endpoints

Tertiary objectives	Endpoints
---------------------	-----------

Determine the rate of successfully established cultures from surgical samples	The percentage of cultures in which $\geq 70\%$ of viable tumour cells encapsulated post-isolation on day 0 are still alive on day 3 in the control cultures (no treatment) compared to the number of tumour samples ( $\geq 0.4g$ ) successfully accepted at Pear Bio's lab.
Determine the rate of successfully cultured immune cells	The percentage of cultures in which $\geq 70\%$ of viable immune cells plated post-extraction on day 0 are still alive on day 3 in the control cultures (no treatment) compared to the number of blood samples ( $\geq 40mL$ ) successfully accepted at Pear Bio's lab.
Find correlations between ex vivo tumour culture or multi-omic biomarkers and real-world patient outcomes	For any cases where patient outcomes are available or become available prospectively, such as recurrence post-surgery, potential predictive or prognostic biomarkers will be identified. As this data will be sparse, the analysis will only be used to generate hypotheses for future trials, if the data allows.
Assess Pear Bio's assay ability to categorise patients for below average or above average overall survival (OS)	
Patient data is collected up to death and their time from diagnosis to death is recorded to determine the overall survival (OS) time.
 
This analysis will use median OS within the study cohort to differentiate patients as generally responsive or resistant to treatment. The analysis will then explore indicators/biomarkers in Pear Bio's test that can identify patients as generally responsive or resistant to treatment, agnostic of the therapeutic choice.

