**Table 1: Schedule of assessments**

Table notes:

1. A redacted histopathology report will be sent to Pear Bio when it is ready (i.e., it does not have to be sent alongside the tissue, blood and other available data from the day of the surgery).
2. Available data is transferred alongside the tumour sample within 24 hours of surgery to Pear Bio's laboratory. Any remaining data will be transferred as soon as feasible, and we will transfer any further imaging at a single timepoint at 12 months after surgery
3. Relating only to research procedures (e.g., taking a volume of blood that is beyond standard care for a given patient). This can be conducted by telephone – physical examination to be done only if clinically indicated.
4. Collected only if available for consenting patients within the study period.
5. Collected only if available for consenting patients within the study period.

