### **5.5.6 Tumour size evaluation**

PEAR-GLIO Protocol v1.0  
3rd March 2023

Measurements will be made by contrast-enhanced MRI. Imaging reports and pseudonymised images will be included as study data collected and transferred to Pear Bio, provided the imaging was done within the period of 3 months prior to surgery or during the follow-up period. Sites will transfer initial imaging shortly after surgery, and again at a single timepoint 12 months after surgery.

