## **7: STATISTICAL CONSIDERATIONS**

### **7.1 Sample size**

A maximum of fifty (50) evaluable patients will be recruited to this study. This study is not formally powered due to the proof-of-concept nature of the study and broad inclusion criteria. However, the number of samples acquired in this study will enable Pear Bio to conduct analytical validation on the robustness of its precision medicine platform in brain cancer.

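### No section fixes when a patient's PFS and OS follow-up ends, and the stops the protocol implies conflict; if sites stop each patient at 12 months, the cohort median OS needed in section 2.3 would usually not be reached

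*Combined protocol and SAP*

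**What the plan says.** Five places in the protocol bear on how long outcomes are followed.

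- Section 2.2 (PFS, secondary): tumour response is measured as clinically indicated and "at all subsequent timepoints until disease progression", under standard of care. Kaplan–Meier curves and low/high biomarker groups are planned.
- Section 2.3 (OS, exploratory): "Patient data is collected up to death and their time from diagnosis to death is recorded". The median OS of the study cohort then labels patients as responsive or resistant.
- Section 5.5.6: "Sites will transfer initial imaging shortly after surgery, and again at a single timepoint 12 months after surgery". Note 2 to Table 1 (section 5.4) says the same about further imaging.
- Table 1, notes 4 and 5 (recurrence follow-up and further therapy): "Collected only if available for consenting patients within the study period".
- Section 7.4: the study ends with the "last patient's last data at a maximum of 12 months post-surgery".

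Section 7.5 rules out imputation but does not mention censoring. No accrual period is stated. On size, section 7.1 says "A maximum of fifty (50) evaluable patients will be recruited to this study" and "This study is not formally powered due to the proof-of-concept nature of the study and broad inclusion criteria".

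**The concern.** These stops cannot all apply. Collection up to death is impossible for anyone alive at close-out. An early recruit's imaging transfer ends at month 12 while the study stays open for later recruits. The study-period wording in the Table 1 notes suggests that the same recruit's recurrence data continue to close-out. A site could reasonably follow any of these.

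What is at stake is the number of deaths and progressions observed, and whether the cohort median OS exists as an estimate. The split in section 2.3 cannot be made without that median. Because no censoring rule is given, a survivor's time to death could also be recorded as not available and dropped under section 7.5, which would bias any survival summary downwards.

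**Working it through.** The protocol states no power, event count or expected median for this cohort, so there is no planned figure to reproduce. The check asks how much the choice of stop matters.

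**Inputs from the protocol.** Section 1.2.2: "Primary brain tumours have a 5-year survival rate of only 12%, and GBM has a median survival of 15 months". Section 7.1: at most 50 evaluable patients. Sections 5.5.6 and 7.4: 12 months after surgery.

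**Assumptions.** Exponential survival timed from surgery; uniform accrual over 12 or 24 months.

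**Step 1. Alive at 12 months.**
- GBM figure: 0.5^(12/15) = 0.574, so 42.6% dead, or 21.3 deaths in 50.
- 5-year figure: 0.12^(12/60) = 0.654, so 34.6% dead, or 17.3 deaths in 50. The implied median is 60 × ln 2 / (−ln 0.12) = 19.6 months.

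**Step 2. Is the median reached if each patient stops at 12 months?** With everyone censored at the same time, the Kaplan–Meier curve reaches 0.5 only if at least 25 of 50 have died.
- P(Bin(50, 0.426) ≥ 25) = 17.8%.
- P(Bin(50, 0.346) ≥ 25) = 1.8%.

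Fifty is a maximum. With 30 patients the chances are 26% and 6%.

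**Step 3. Other survival shapes.** For a Weibull with shape k, S(12) is exp(−ln 2 × (12/15)^k) for the GBM figure and 0.12^((12/60)^k) for the 5-year figure.

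| Anchor | Dead at 12 months, k = 0.7 to 1.5 | Chance median reached |
|---|---|---|
| GBM, median 15 months | 45% down to 39% | 27% down to 8% |
| 12% alive at 5 years | 50% down to 17% | 54% down to about 0% |

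The 54% needs k = 0.7; k = 0.8 gives 25%. A Weibull through both anchors (k = 0.81) gives 44.0% dead and a 23.5% chance.

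**Step 4. Common close-out at the last patient's month 12.** Simulated studies of 50 patients, with small differences depending on how the last entry date is set:

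| Assumed accrual | GBM: dead / median reached | 5-year: dead / median reached |
|---|---|---|
| 12 months | 55–56% / 94–95% | 46–47% / 68–70% |
| 24 months | about 65% / over 99% | 55–56% / 97–98% |

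**Step 5. Does reaching the median make the split workable?** A patient censored alive before the median cannot be placed on either side of it. With accrual A, hazard λ and true median m, that share is (S(12) − 0.5)/(λA), provided m − 12 ≤ A.
- A = 12: (0.574 − 0.5)/(0.0462 × 12) = 13%, and (0.654 − 0.5)/(0.0353 × 12) = 36%.
- A = 24: half of these, 7% and 18%.

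Measured against the estimated median in simulated studies that reach it, the share is about 8% to 29%.

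**The case against.** The strongest reply is that the protocol never stops survival follow-up at 12 months for each patient. Section 5.5.6 and note 2 restrict imaging transfer, not vital status or recurrence. Section 7.4 is set by the last patient. Table 1 schedules data transfer at follow-up and at recurrence without a 12-month limit. This stands. A reader might infer that 12 months is the cut for everyone and that the median will usually not be reached; the documents do not support that unconditionally. The reply does not remove the gap, because no passage says that earlier recruits are followed to close-out, and section 2.3 still promises more than section 7.4 allows.

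A reader might also infer a comparable loss of PFS events. The documents cannot support a size, because they give no PFS figure. Assumed medians of 6 to 9 months put 60% to 75% of patients past progression by month 12. Section 2.2's wording is also tied to standard of care and describes clinical assessment more than data collection, so the conflict there is weaker than for OS.

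The anchors are imperfect too. OS is timed from diagnosis and section 3.1 admits previously treated patients, so month 12 after surgery is not month 12 on the OS clock. Neither survival figure describes this case mix.

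Finally, section 1.1 says patient outcomes get no formal statistical analysis, section 3.3 lists follow-up outcomes as collected if available, and PFS and OS are secondary and exploratory. That limits the weight of the point. Descriptive curves still need a cut-off and a censoring rule.

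**Conclusion.** The point holds in conditional form. The stops in sections 2.3, 5.4 (note 2), 5.5.6 and 7.4 are not reconciled, and no per-patient cut-off or censoring rule is stated. A 12-month stop per patient gives about an 18% (GBM figure) or 2% (5-year figure) chance of reaching the cohort median OS with 50 patients, and 8–27% or about 0–54% across the Weibull shapes tried. Follow-up to the last patient's month 12 gives about 95% or 70% with 12 months' accrual and 97–100% with 24. These figures rest on survival timed from surgery, on background rates that may not match the cohort, and on accrual lengths the protocol does not give. No PFS magnitude is claimed. The primary laboratory objective is untouched. This is a worthwhile, cheap correction to hypothesis-generating aims, not a threat to the study's main result.

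**What to change.** 1. Reconcile sections 2.2, 2.3, 5.4 note 2, 5.5.6 and 7.4 to one common data cut-off: the date the last patient reaches 12 months after surgery.
2. At that date, collect one final status record for every patient: date last known alive, date last known progression-free, event dates, and reports of any standard-of-care imaging since the 12-month transfer. Censor event-free patients at the cut-off, or at the last known status date if that is earlier.
3. State the time origin for PFS and OS. If OS stays timed from diagnosis, treat patients as entering the risk set at study surgery (delayed entry).
4. Replace the responsive/resistant split at median OS with time-to-event analysis of the ex vivo metrics (Kaplan–Meier by low/high group, or Cox), and report 12-month OS and PFS with confidence intervals. Patients censored before the median cannot be classified even when it is reached, so a later cut-off alone does not rescue the split.

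The cost is a wording amendment and one extra chart-status request per patient at close-out. Inclusion criterion 6 already covers consent to outcome data, the end-of-study date does not move, and no patients, visits or scans are added. Follow-up length will differ between early and late recruits, which censoring handles.

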## **7.5 Handling of missing data**

Missing data will be recorded as not available on eCRFs. Missing data points will not be imputed in the analysis for that specific endpoint.

## **8: DATA HANDLING AND RECORD KEEPING**

### **8.1 Confidentiality**

All information generated in the study will be kept strictly confidential. The researchers conducting the trial will abide by the Data Protection Act 1998, and the rights the patient has under this act.

Parts of the patients' medical records and the data collected for the trial will be looked at by authorised personnel from the Sponsor. It may also be looked at by authorised personnel from the patient's NHS Trust to check that the trial is being carried out correctly. This is clearly stated on the consent form.

All the above bodies have a duty of confidentiality to the patient as a research participant and nothing that could reveal their identity will be disclosed outside the research site. All data will be stored in a locked and dedicated room only accessible by authorised personnel.

### **8.2 Study documents**

All trial related documents should be filed in the Investigator's Site File (ISF). It should contain essential documents as per the contents page provided to the Investigator by the Sponsor. The Sponsor will inform the PI and their staff of any updates and forward any relevant documentation. It is the participating PI's responsibility to maintain this file and keep all records up to date.

### **8.3 Data and sample acquisition**

This trial uses electronic case report forms (eCRFs). Sites will receive training for appropriate eCRF completion. The eCRFs will be submitted electronically to the Sponsor and should be handled in accordance with the Sponsor's instructions. Any data queries arising from initial review will be sent to the relevant centre for resolution.

All eCRFs should be completed by designated, trained examining personnel or the study coordinator as appropriate. The eCRF should be reviewed and electronically signed and dated by the investigator. In addition, at the end of the study, the investigator will receive patient data for his or her site that must be kept with the study records.

The Trial Management Group (TMG) reserves the right to amend or add to the eCRFs as appropriate. Revised or additional forms should be used by centres in accordance with the guidelines provided by the Sponsor.

The PI will be responsible for monitoring the transfer of biological specimens. The Sponsor will confirm the receipt of biological specimens. Tracking forms will accompany all sample transfers to the Sponsor's central lab. The clinical site will link with the Sponsor to ensure all

biological samples are collected and transferred as per the lab manual. All data will be handled, computerised and stored in accordance with GDPR.

PPIE work will take place within the host NHS Trust, and any notes will be kept securely by the clinical team. Any results will be provided in an anonymised, summarised format only. Staff from the Sponsor may be invited to take part in these sessions in order to explain the product in detail, but will not be allowed to collect identifiable data on any participants.

#### **8.4 Record retention and archiving**

At the end of the trial, all documentation, as defined by GCP, should be stored by each individual site's archiving facility, until notification for destruction from the Sponsor. The location of the archiving facility must be provided to the Sponsor.

The Sponsor will arrange a 'close out' visit where all trial documentation will be prepared for archiving by that site. Records will be retained at each individual site. All records relating to the trial should be stored together, including the ISF. It is the responsibility of the Principal Investigator to ensure a full set of records is collated and documented.

In addition, source documentation (medical notes, images, results etc.) should be retained, as per Sponsor request, for the duration of the archiving period.

All this information will be stored for a minimum of 25 years. The Sponsor should be contacted prior to destruction.

#### **8.5 Compliance**

This trial will be conducted in accordance with the principles of Good Clinical Practice (GCP) as laid out in the EU directive and The Medicines for Human Use (Clinical Trials) Regulation 2004, and its amendments.

In addition, Sponsor auditors will be allowed access to eCRFs, source documents, and other trial files to evaluate the trial. Audit reports will be kept confidential.

### **9: STUDY MANAGEMENT**

A TMG will be convened and will consist of members of the clinical coordinating centre (CI, Trial Coordinator, Clinical Research Fellow) and the Sponsor's representatives, scientists and statistician(s). The role of the TMG will be to monitor all aspects of the conduct and progress of the trial, ensure that the protocol is adhered to, and take appropriate action to safeguard participants and the quality of the trial itself. The TMG will meet at least twice a year. Final decisions about the continuation or termination of the trial are the responsibility of the TMG.

### **10: CLINICAL GOVERNANCE ISSUES**

#### **10.1 Ethical considerations**

The trial will be conducted in accordance with ethical principles founded in the Declaration of Helsinki. The Research Ethics Committee (REC) will review all appropriate trial documentation in order to safeguard the rights, safety and wellbeing of patients. The trial will only be conducted at sites where appropriate approval has been obtained.

The Sponsor will inform the REC of any changes to the conduct of the trial and seek approval for these changes and any amended patient materials. The Sponsor will maintain an accurate and complete record of all written correspondence to and from the REC and will agree to share all such documents and reports with the Sponsor.

The informed consent and any other documentation provided to patients will be revised if important new information becomes available that is relevant to the subject's consent. Amended documents will be approved by the REC before distribution to patients.

Participation in the PPIE stream will be by invitation, and participants will be provided with written information on background, purpose and use of data from the sessions.

## **10.2 Summary of monitoring plan**

Refer to the PEAR-GLIO Monitoring Plan for further details. Monitoring will involve a review of the Investigator Site File (ISF), as well as a proportion of Source Data Verification (SDV). This will involve direct access by Sponsor representatives (or other parties, see Section 8.1) to patient notes at the participating hospital sites, which will include the review of consent forms and other relevant investigational reports. Missing data will be sought, unless confirmed as not available. During these visits, the site's activity will be monitored to verify that:

- Source data transcribed onto eCRFs is authentic, accurate, and complete
- Safety, rights, and well-being of the participants are being protected
- The study is being conducted in accordance with the currently approved protocol
- Any other study agreements, GCP, and all applicable NRES requirements are met

